Investigational Product (Test lens): The test product will be rotationally stabilized astigmatic soft contact lenses in senofilcon A with a chromophore to filter High-Energy Visible Light (HEVL). Approved Product (Control lens): The control product will be DAILIES TOTAL1® for Astigmatism Contact Lenses (DT1fA).		
Wear Schedule: Daily wear		
Replacement Schedule: Daily disposable		
Primary Objective: The primary objective of this study is to estimate the incidence rate (percentage) of eyes with clinically significant slit-lamp findings (Grade 3 or 4) related to each study lens (Test lens and Control lens) after approximately 2-weeks of lens wear.		
Exploratory Objectives: The exploratory objectives of this study include the estimation of the mean difference between study lenses (Test lens and Control lens) with respect to distance monocular high luminance, high contrast (HLHC), logMAR visual acuity (at the 1-week follow-up visit), and CLUE comfort, vision, and handling scores (at the fitting, 1- and 2-week follow-up visits). Additional exploratory objectives of the study are to estimate the mean and standard deviation of the mean settled toric orientation of each study lens (Test lens and Control lens) following lens settling and after 1- and 2-weeks of lens wear, and to assess the toric lens orientation of each study lens, 1- and 3-minutes after lens insertion. Adverse events will also be monitored and collected.		
Primary endpoint: • Indicidence (percentage) of eyes with Grade 3 or 4 slit lamp findings related to the study lenses (Test lens and Control lens) after 2-week of lens wear. Exploratory endpoints: • Distance Monocular HLHC logMAR at 4m at the 1-week follow-up visit • Contact Lens User Experience (CLUE) comfort scores at the fitting, 1-, and 2-week follow-up visits • CLUE vision scores at the fitting, 1-, and 2-week follow-up visits • CLUE handling scores at the fitting, 1-, and 2-week follow-up visits • Lens orientation at 1 minute and 3 minutes following insertion at fitting • Mean Settled Lens Orientation at the fitting, 1-, and 2-week follow-up visits		

Study Design	This will be a multi-site, bilateral, dispensing, randomized, controlled, double-masked, 2×2 crossover study. Eligible subjects will be randomly assigned to one of two lens wear sequences (Test/Control or Control/Test). Each lens will be worn for a period of 14(±4) days. There will be a 7(±2) days washout period between study lenses. There will be a total of 6 visits: Visit 1: Screening, baseline evaluation and lens fit #1 Visit 2: Follow-up evaluation #1 (for first lens dispensed) Visit 3: Follow-up evaluation #2 (for first lens dispensed) Visit 4: Continuance, lens fit #2 Visit 5: Follow-up evaluation #3 (for second lens dispensed) Visit 6: Follow-up evaluation #4 (for second lens dispensed) See the flow chart at the end of the synopsis table for a schematic of the
Sample Size	study visits and procedures (Figure 1). This study will have an enrollment target of approximately 66 subjects, with
Sample Size	a target of at least 60 to complete (assuming a dropout rate of 10%).
Study Duration	Total study duration including the enrollment period is anticipated to be approximately 10 weeks.
Anticipated Study Population	Subjects will be habitual soft contact lens wearers with bilateral astigmatism who are between 18 and 39 years of age (inclusive).
Eligibility Criteria - Inclusion	Potential subjects must satisfy of all the following criteria to be enrolled in
	Inclusion Criteria following Screening The subject must: 1. Read, understand, and sign the STATEMENT OF INFORMED CONSENT and receive a fully executed copy of the form. 2. Appear able and willing to adhere to the instructions set forth in this clinical protocol. 3. Be between 18 and 39 (inclusive) years of age at the time of screening. 4. By self-report, habitually wear soft contact lenses in both eyes in a daily reusable or daily disposable wear modality (i.e., not extended wear modality). Habitual wear is defined as a minimum of 6 hours of wear per day, for a minimum of 2 days per week during the past four weeks. 5. Possess a wearable pair of spectacles that provide correction for distance vision. Inclusion Criteria at Baseline Evaluation The subject must: 6. In both eyes, have refractive error suitable for correction with the toric contact lens powers available in this study: a. Sphere powers (DS) -1.50 through -4.00 in 0.25 steps b. Cylinder powers (DC) -0.75 and -1.25 c. Axes (°) 170, 180, 10, 80, 90, 100 7. Have best corrected monocular distance visual acuity of 20/30 or better in each eye.

Eligibility Criteria – Exclusion	Potential subjects who meet any of the following criteria will be excluded from participating in the study:
	Exclusion Criteria following Screening The subject must not:
	1. Be currently pregnant or lactating.
	2. Be diabetic.3. Be currently using any ocular medications or have any ocular infection
	of any type.
	 By self-report, have any ocular or systemic disease, allergies, infection, or use of medication that might contraindicate or interfere with contact lens wear, or otherwise compromise study endpoints, including infectious disease (e.g., hepatitis, tuberculosis), contagious immunosuppressive disease (e.g., Human Immunodeficiency Virus [HIV]), autoimmune disease (e.g., rheumatoid arthritis, Sjögren's syndrome), or history of serious mental illness or seizures. See section 9.1 for additional details regarding excluded systemic medications. Have habitually worn rigid gas permeable (RGP) lenses, orthokeratology lenses, or hybrid lenses (e.g., SynergEyes, SoftPerm) within the past 6 months. Be currently wearing monovision or multifocal contact lenses. Be currently wearing lenses in an extended wear modality. Have a history of strabismus or amblyopia. Be an employee (e.g., Investigator, Coordinator, Technician) or immediate family member of an employee (including partner, child, parent, grandparent, grandchild or sibling of the employee or their spouse) of the clinical site. Have participated in a contact lens or lens care product clinical trial
	within 7 days prior to study enrollment.
	Exclusion Criteria at Baseline Evaluation
	The subject must not:
	11. Have clinically significant (grade 3 or higher on the FDA grading scale) slit lamp findings (e.g., corneal edema, neovascularization or staining, tarsal abnormalities or bulbar injection) or other corneal or ocular disease or abnormalities that contraindicate contact lens wear or may otherwise compromise study endpoints (including entropion, ectropion, chalazia, recurrent styes, glaucoma, history of recurrent corneal erosions, aphakia, moderate or above corneal distortion, herpetic keratitis).
	12. Have fluctuations in vision due to clinically significant dry eye or other
	ocular conditions.
	13. Have had or have planned (within the study period) any ocular or intraocular surgery (e.g., radial keratotomy, PRK, LASIK, iridotomy, retinal laser photocoagulation, etc.).
Disallowed	Subjects will not be eligible to enroll if they are taking any ocular
Medications/Interventions	medications, or any systemic medications that would normally contraindicate contact lens wear or may otherwise compromise study endpoints. See section 9.1 for details regarding disallowed systemic medications.

Measurements and Procedures	The key procedures associated with the endpoints for this study will be:		
110000010110110001100000000000000000000	- Examination of the anterior segment using a slit lamp biomicroscope and grading findings using the FDA grading scale		
	- Measurement of HLHC VA using ETDRS charts		
	- Measurement of toric lens orientation and rotational stability using a slit		
	lamp biomicroscope		
	- Overseeing completion of the CLUE questionnaires		
Microbiology or Other	Not applicable for this study.		
Laboratory Testing			
Study Termination	The occurrence of an Unanticipated Adverse Device Effect (UADE) or		
	Serious Adverse Event (SAE) for which a causal relationship to a test article		
	cannot be ruled out, will result in stopping further dispensing investigational		
	product. In the event of a UADE or SAE, the Sponsor Medical Monitor may		
	unmask the treatment regimen of subject(s) and may discuss this with the		
	Principal Investigator before any further subjects are enrolled.		
Ancillary Supplies/ Study-	Lens cases, fluorescein strips and preservative-free rewetting drops /		
Specific Materials	artificial tears will be supplied for use as needed.		
Principal Investigator(s) and	A full list of Principal Investigators, clinical sites, and institutions is kept		
Study Institution(s)/Site(s)	separately from the Study Protocol and is included in the study Trial Mast		
	File.		

Figure 1: Study Flowchart

COMMONLY USED ABBREVIATIONS, ACRONYMS AND DEFINITIONS OF TERMS

ADE Adverse Device Effect

ADHD Attention Deficit Hyperactivity Disorder
AE Adverse Event/Adverse Experience
BSCVA Best Spectacle Corrected Visual Acuity

CFR Code of Federal Regulations
CLUE Contact Lens User Experience
COM Clinical Operations Manager
CRA Clinical Research Associate

CRF Case Report Form

CRO Contract Research Organization

D Diopter

DMC Data Monitoring Committee eCRF Electronic Case Report Form EDC Electronic Data Capture

ETDRS Early Treatment Diabetic Retinopathy Study

FDA Food and Drug Administration GCP Good Clinical Practice HEVL High Energy Visible Light

HIPAA Health Insurance Portability and Accountability Act

HIV Human Immunodeficiency Virus

IB Investigator's Brochure

ICH The International Council for Harmonization

IDEInvestigational Device ExemptionIECIndependent Ethics CommitteeIRBInstitutional Review Board

ISO International Organization for Standardization

ITT Intent-to-Treat

JJVC Johnson & Johnson Vision Care, Inc.

LASIK Laser-Assisted in Situ Keratomileusis

LogMAR Logarithm of Minimal Angle of Resolution

OD Right Eye
OS Left Eye
OU Both Eyes

PIG Patient Instruction Guide
PQC Product Quality Complaint
PRK Photorefractive Keratectomy
PRO Patient Reported Outcome

QA Quality Assurance

SAE Serious Adverse Event/Serious Adverse Experience

SAP Statistical Analysis Plan
SAS Statistical Analysis System
SD Standard Deviation
SLF Slit Lamp Finding

UADE Unanticipated Adverse Device Effect
USADE Unanticipated Serious Adverse Device Effect

VA Visual Acuity

1. INTRODUCTION AND BACKGROUND

DAILIES TOTAL1® for Astigmatism Contact Lenses (DT1fA) are single-use, daily disposable lenses indicated for the correction of astigmatism and associated ametropia in persons with non-diseased eyes. The purpose of this study is to evaluate the ocular physiological response following wear of a daily disposable, toric lens design in senofilcon A incorporating a HEVL-filtering chromophore (RTY-1) relative to DT1fA as Control.

1.1. Name and Descriptions of Investigational Products

The Test lens in this study will be a toric contact lens design in senofilcon A containing a HEVL-filtering chromophore (RTY-1).

The Control lens in this study will be DT1fA. DT1fA contact lenses are made from a lens material that is 33% water and 67% (delefilcon A) polymer, a silicone containing hydrogel with added phosphatidylcholine. DT1fA lenses also contain a handling tint (color additive copper phthalocyanine).

Further details about the Test and Control articles are found in section 6.1 of this protocol, the Investigator's Brochure⁴ and in the DT1fA package insert (Appendix C).

1.2. Intended Use of Investigational Products

The intended use of the investigational products is the correction of astigmatism and associated myopic refractive error. Study lenses will be worn bilaterally in a daily wear, daily disposable modality for at least 8 hours per day. Each wear period will be 14±4 (i.e., 10 to 18) days in duration, and subjects will be instructed to wear lenses for at least 5 days per week during each wear period. Two wear periods will be completed, with a washout period of 7±2 days between the wear periods.

1.3. Summary of Findings from Nonclinical Studies

All previous pre-clinical findings for the test lens were deemed satisfactory prior to proceeding with clinical trials on humans. For the most comprehensive nonclinical information regarding the test design refer to the Investigator's Brochure.⁴

1.4. Summary of Known Risks and Benefits to Human Subjects

The anticipated clinical benefit of the investigational lenses will be the correction of refractive error. No adverse device effects are anticipated. The risks associated with use of the investigational lenses are considered to be the same as those for other marketed soft contact lens worn in the same modality (i.e., daily disposable wear). No additional risks associated with participation in this investigation are anticipated.

Comprehensive risk and benefit information regarding the investigational (test lens) design and the DT1fA control lens are included in the Investigator's Brochure⁴ and the DT1fA package insert (Appendix C), respectively.

1.5. Relevant Literature References and Prior Clinical Data Relevant to Proposed Clinical Study

Prototype toric lens designs featuring the RTY-1 chromophore have previously been evaluated in several JJVC-sponsored clinical trials. Safety data from these trials suggest the investigational lenses have a safety profile equivalent to currently marketed soft contact lens products; a review of literature references and prior clinical data related to the test designs is given in the Investigator's Brochure.⁴

DT1fA contact lenses are approved in the US for the correction of astigmatism and associated ametropia in persons with non-diseased eyes. For further details regarding the DT1fA control lens, refer to the DT1fA package insert (Appendix C).

CR-6553, v3.0 JJVC CONFIDENTIAL

2. STUDY OBJECTIVES, ENDPOINTS AND HYPOTHESES

2.1. Objectives

Primary Objective:

The primary objective of this study is to estimate the incidence rate (percentage) of eyes with clinically significant slit-lamp findings (Grade 3 or 4) related to each study lens (Test lens and Control lens) after approximately 2-weeks of lens wear.

Exploratory Objectives:

The exploratory objectives of this study include the estimation of the mean difference between study lenses (Test lens and Control lens) with respect to distance monocular high luminance, high contrast (HLHC), logMAR visual acuity (at the 1-week follow-up visit), and CLUE comfort, vision, and handling scores (at the fitting, 1- and 2-week follow-up visits). Additional exploratory objectives of the study are to estimate the mean and standard deviation of the settled toric roation of each study lens (Test lens and Control lens) following lens settling and after 1- and 2-weeks of lens wear, and to assess the toric lens orientation of each study lens, 1- and 3-minutes after lens insertion. Adverse events will also be monitored and collected.

2.2. Endpoints

Primary endpoint:

1. Percentage of Eyes with slit-lamp findings (Grade 3 or 4) related to study lens wear

Slit Lamp Findings (Grade 3 or higher) will be assessed for each subject eye at all study visits (scheduled and unscheduled). However, the primary endpoint will be the percentage of eyes with Grade 3 or higher SLFs related to study lens wear, after approximately 2 weeks of lens wear.

SLFs will be evaluated and classified using the FDA Grading scale rating from 0 to 4, where Grade 0 represents the absence of findings and 1 to 4 representing successively worse findings (i.e., Grade 1=trace, Grade 2= mild, Grade 3=moderate and Grade 4= severe).

Exploratory Endpoints:

1. Distance Monocular HLHC logMAR Visual Acuity

Visual acuity (VA) will be assessed monocularly at the 1-week follow-up visits under high-luminance high contrast (HLHC) conditions at a test distance of 4 meters using ETDRS Charts. The logMAR VA score is a continuous endpoint.

2. CLUE Comfort Scores

Subjective comfort will be assessed using the Contact Lens User Experience (CLUE) questionnaire. CLUE will be assessed at the fitting, 1- and 2-week follow-up visits. The CLUE comfort score is a conintuous endpoint.

CLUE is a validated patient-reported outcomes questionnaire to assess patient-experience attributes of soft, disposable contact lenses (comfort, vision, handling, and packaging) in a contact-lens wearing population in the US, ages 18-65. Derived CLUETM scores using Item Response Theory (IRT) follow a normal distribution with a population average score of 60 (SD 20), where higher scores indicate a more favorable/positive response with a range of 0-120. A 5-point increase in an average CLUETM score translates into 10% shift in the distribution of scores for population of soft contact lens wearers.⁵

- 3. CLUE Vision Scores at the fitting, 1-, and 2-week follow-up visits. The CLUE vision score is a conintuous endpoint.
- 4. CLUE Handling Scores at the fitting, 1-, and 2-week follow-up visits. The CLUE handling score is a conintuous endpoint.

CR-6553, v3.0 JJVC CONFIDENTIAL

5. Toric Lens Orientation

Toric lens orientation (scribe mark position relative to 6 o'clock) will be assessed for each eye at 1, 3 and at least 15 minutes after lens insertion at the fitting visit, and at the 1- and 2-week follow-up visits. However, toric lens orientation at 1- and 3-minutes after lens insertion at the fitting visit is the exploratory endpoint. The endpoint is the distribution (counts, percentages) of eyes for the toric Orientation (in degrees).

6. Mean Settled Lens Orientation

Lens orientation (scribe mark position relative to 6 o'clock) will be assessed for each eye at 1 minute, 3 minutes, at least 15 minutes after lens insertion; 2 additional measurements per eye following settling will also be collected. The exploratory endpoint is the lens orientation assessed at the fitting, 1-, and 2-week follow-up visits. Mean settled lens orientation is a continuous response where the mean is calculated by eye by averaging across all lens orientation measurements collected at least 15-minutes after lens insertion. The standard deviation of average settled lens orientation will also be calculated. See in Appendix D for details regarding the collection of lens orientation.

7. Adverse events (AEs) - including ocular and non-ocular. Details for AEs will be provided through listings.

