1.30.	Schedule next visit	Schedule the next visit to occur in 7(±2) days (counting the day of this visit as day 0, the subject may return on day 5 through 9). Ensure the subject is instructed to wear the study lenses for at least 1 hour immediately prior to attending the next visit.			

VISIT 2

Visit 2 will occur 5 to 9 days following Visit 1. Subjects must present to this visit wearing the study lenses in both eyes, and lenses must have been worn for at least 1 hour prior to the visit.

		Visit 2: Follow-Up #	1			
Step	Procedure	Details				
2.1.	Wear time and compliance	Record the subjects wearing time and comfortable wearing time. Subjects must have worn lenses for at least 8 hours on at least 5 days between the dispensing visit and this visit, and for at least 1 hour prior to attending this visit.				
2.2.	Review medical history and concomitant medications	Record any changes to the (including adverse events medications.				
2.3.	Subject reported ocular symptoms	Record any subject repor response to a verbal oper questionnaire.				
2.4.	Follow-up PRO questionnaire	Subjects will complete a PRO questionnaire to assess their experience with the study lenses. The glare PRO questionnaire will be completed first, followed by the CLUE questionnaire, followed by the other PRO items.				
2.5.	Entrance visual acuity	Record the entrance Snel wearing the study lenses.		ch eye while		
2.6.	Distance ETDRS visual acuity	Measure monocular discontrast (HLHC) visual 4 meters. Measure each eye using below:	acuity using E	TDRS charts	at	
		Condition	HI	HC		
		Room illumination	> 40	0 lux		
		Chart luminance	120 - 20	00 cd/m ²		
		Eye	OD	os		
		Charts	HC-1	HC-2		
2.7.	Toric lens orientation	Recorded letter-by-letter results into EDC. Record the toric lens orientation for each eye to the nearest degree.				
2.8.	Lens removal	Remove and place both lenses into a lens case with saline solution. Do not discard the lenses.				

Visit 2: Follow-Up #1			
Step	Procedure	Details	
2.9.	Biomicroscopy	The FDA Slit Lamp Classification Scale will be used to grade findings. If any slit lamp finding is graded as 3 or worse, the subject must be discontinued, an adverse event will be recorded, and the subject will be monitored as per the guidelines given in section Error! Reference source not found Should the clearance of the fluorescein need to be expedited, preservative-free rewetting drops or artificial tears may be instilled.	

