4.4.	Remove habitual lenses (if worn)	If worn, the subject's habitual contact lenses will be removed. Lenses may be stored in a lens case, if required.	
4.5.	Biomicroscopy	The FDA Slit Lamp Classification Scale will be used to grade findings. If any slit lamp finding is graded as 3 or worse, the subject must be discontinued, an adverse event will be recorded and the subject will be monitored as per the guidelines given in section Error! Reference source not found.	
		Should the clearance of the fluorescein need to be expedited, preservative free rewetting drops or artificial tears may be instilled.	
4.6.	Continuance	Verify that the subject is eligible to continue in the study.	V S

Visit 4: Lens Fitting #2

The steps followed will be the same as those listed under Visit 1: Lens Fitting #1.

VISIT 5

Visit 5 will occur 5 to 9 days following Visit 4. Subjects must present to this visit wearing the study lenses in both eyes, and lenses must have been worn for at least 1 hour prior to the visit.

Visit 5: Follow-Up #3

The steps followed will be the same as those listed under Visit 2: Follow-Up #1.

VISIT 6

Visit 6 will occur 5 to 9 days following Visit 5. Subjects must present to this visit wearing the study lenses in both eyes, and lenses must have been worn for at least 1 hour prior to the visit.

Subjects should bring their own habitual spectacles or contact lenses to this visit to wear following study lens removal.

Visit 6: Follow-Up #4			
Step	Procedure	Details	
6.1.	Wear time and compliance	Record the subjects wearing time and comfortable wearing time. Subjects must have worn lenses for at least 8 hours on at least 5 days during the dispensing period, and for at least 1 hour prior to attending this visit.	
6.2.	Collect unworn lenses	Collect any unworn study lenses that were dispensed at the previous visit.	
6.3.	Review medical history and concomitant medications	Record any changes to the subject's medical history (including adverse events) or concomitant medications.	
6.4.	Subject reported ocular symptoms	Record any subject reported ocular symptoms in response to a verbal open-ended symptoms questionnaire.	
6.5.	Follow-up PRO questionnaire	Subjects will complete a PRO questionnaire to assess their experience with the study lenses.	
		The glare PRO questionnaire will be completed first, followed by the CLUE questionnaire, then the other PRO items, then the preference questionnaire.	

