8.2. Withdrawal/Discontinuation from the Study

A subject will be withdrawn from the study for any of the following reasons:

- Subject withdrawal of consent.
- Subject not compliant to protocol.
- Subject lost to follow-up.
- Subject no longer meets eligibility criteria (e.g. the subject becomes pregnant).
- Subject develops significant or serious adverse events necessitating discontinuation of study lens wear.
- Subjects who have experienced a Corneal Infiltrative Event (CIE).
- Investigator's clinical judgment regarding the subject safety reasons (that it is in the best interest of the subject to stop treatment).
- Subject misses any study visits.
- Subject not compliant with study lens wear schedule.
- Subject not successfully dispensed due to lack of efficacy and safety including poor vision, poor comfort or unacceptable fit.

For discontinued subjects, the Investigator will:

- Complete the current visit (scheduled or unscheduled).
- Complete the Final Evaluation, indicating the reason that the subject was discontinued from the study.
- Record the spherocylindrical refraction with best corrected distance visual acuity.
- Collect used test article(s) (worn or brought to the visit) from the subject and discard them, unless otherwise stated in section 7.2.
- Collect all unused test article(s) from the subject.
- Make arrangements for subject care, if needed, due to their study participation.

Additional subjects may be enrolled if a subject discontinues from the study prematurely.

In cases where a subject is lost to follow-up, every possible effort must be made to contact the subject and determine the reason for discontinuation/withdrawal. The measures taken to follow up must be documented including two written attempts and a certified letter (or equivalent) as the final attempt.

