Diagnoses and conditions that are considered Ocular Significant Adverse Events include, but not limited to the following:

- Contact Lens Induced Peripheral Ulcer (CLPU)
- Significant Infiltrative Events (SIE)
- Superior Epithelial Arcuate Lesions (SEALs)
- Any Temporary Loss of > 2 Lines of BSCVA
- Other grade 3 or higher corneal findings, such as abrasions or edema
- Non-contact lens related corneal events e.g. Epidemic Keratoconjunctivitis (EKC)
- Asymptomatic Corneal Scar
- Any corneal event which necessitates temporary lens discontinuation > 2 weeks

Non-Significant Adverse Events – are defined as those events that are usually asymptomatic and usually do not warrant discontinuation of contact lens wear but may cause a reduction in wear time. However, the Investigator may choose to prescribe treatment as a precautionary measure.

Diagnoses and conditions that are considered Ocular Non-Significant Adverse Events include, but not limited to the following:

- Non-significant Infiltrative Event (NSIE)
- Contact Lens Papillary Conjunctivitis (CLPC)
- Superficial Punctate Keratitis (SPK)
- Conjunctivitis: Bacterial, Viral, Allergic
- Blepharitis
- Meibomianitis
- Contact Dermatitis
- Localized Allergic Reactions
- Any corneal event not explicitly defined as serious or significant adverse event, which necessitates temporary lens discontinuation < 2 weeks

Adverse Device Effect (ADE) – An ADE is an "adverse event related to the use of an investigational medical device."

NOTE 1: This definition includes adverse events resulting from insufficient or inadequate instructions for use, deployment, implantation, installation, or operation, or any malfunction of the investigational medical device. **NOTE** 2: This definition includes any event resulting from use error or from intentional misuse of the investigational medical device.

Unanticipated Adverse Device Effect (UADE) – A UADE is any serious adverse effect on health or safety or any life-threatening problem or death caused by, or associated with, the test article, if that effect, problem, or death was not previously identified in nature, severity, or degree of incidence in the investigational plan, Investigator's Brochure or protocol, or any other unanticipated serious problem associated with the test article that relates to the rights, safety and welfare of subjects.

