14. STATISTICAL METHODS

14.1. General Considerations

Statistical Analysis will be undertaken by the sponsor or under the authority of the sponsor. A general description of the statistical methods to be implemented in this clinical trial is outlined below.

Descriptive statistics will be reported for all key variables as appropriate. Continuous data will be summarized descriptively by sample size (n), mean, standard deviation (SD), median, minimum (Min) and maximum (Max). Categorical data will be summarized descriptively by frequency count (n) and percentage (%) of subjects or eyes within each category level. Summary tables will be presented by event (Baseline, Fitting, 1-week follow-up, 2-week follow-up, Unscheduled and Final Evaluations) and study lens type (Test and Control) as applicable, for the analysis set of interest. The denominator for all percentages will be the number of subjects (or eyes as applicable) with available data in the lens group under consideration. Unscheduled visits and tele-visits will be summarized separately and will be excluded from the primary and secondary analysis.

All available data collected at scheduled visits will be used in the statistical summaries and analyses, with no imputation of missing data. Unscheduled visits will be summarized separately and will be excluded from the statistical analysis. All data summaries and statistical analyses will be performed using the SAS software Version 9.4 or higher (SAS Institute, Cary, NC).

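### The 2-week primary percentage omits lens-related Grade 3+ findings that arise before the 2-week visit, so it understates incidence if any occur

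*Combined protocol and SAP*

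**What the plan says.** The primary objective (Section 2.1) is to estimate, for each lens, the incidence of eyes with lens-related Grade 3 or 4 slit-lamp findings after about two weeks of wear. Section 2.2 first says that such findings are assessed at every scheduled and unscheduled visit. It then narrows the endpoint with the word However: "the primary endpoint will be the percentage of eyes with Grade 3 or higher SLFs related to study lens wear, after approximately 2 weeks".

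The procedures and analysis rules that bear on this are:

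- **Section 7.2, step 2.9 (1-week visit, Visit 2):** "If any slit lamp finding is graded as 3 or worse, the subject must be discontinued". An adverse event is also recorded. For Visit 5, the 1-week visit on the second lens, "The steps followed will be the same as those listed under Visit 2: Follow-Up #1".
- **Section 13.1:** the ocular significant adverse events include "Other grade 3 or higher corneal findings, such as abrasions or edema".
- **Section 8.2:** one reason for withdrawal is "Subject develops significant or serious adverse events necessitating discontinuation of study lens wear".
- **Section 14.1:** "The denominator for all percentages will be the number of subjects (or eyes as applicable) with available data" in the lens group; and "Unscheduled visits and tele-visits will be summarized separately and will be excluded from the primary and secondary analysis". Tables are by event, with 1-week, 2-week, unscheduled and final evaluation shown separately.
- **Section 14.5:** the primary endpoint is summarised on the Safety population as a distribution of grades by lens. No visit is named, and nothing is said about findings before week 2.
- **Section 14.9:** missing values are not imputed, and their counts are tabulated.

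**The concern.** The event that the study sets out to count also removes the subject from the examination at which it is counted. An eye that reaches Grade 3 at one week is an event by the study's own definition, yet step 2.9 ensures that it has no 2-week examination on that lens. The missing value is caused by the outcome, so leaving it out is not neutral. The fellow eye leaves with it.

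Findings between scheduled visits raise a related problem. Section 14.1 keeps them out of the primary analysis whether or not the subject continues. If the subject stays in the study and the finding resolves by week 2, the eye counts as event-free. If the subject is withdrawn, the eye disappears from the 2-week percentage.

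No hypothesis or threshold depends on this percentage (Sections 2.3 and 14.4). The estimate and its precision are therefore the whole primary result, and with 0, 1 or 2 events planned for in Table 7, one misplaced event matters.

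**Working it through.** **Inputs.** Section 14.2: 60 completers, 120 eyes, with Table 7 scenarios of 0, 1 and 2 events. The denominator and missing-data rules come from 14.1 and 14.9, and the discontinuation rule from step 2.9. The documents give no early-event rate, so k, the number of subjects withdrawn from a lens with an early related Grade 3+ finding, is an assumption shown as a range.

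**Reproducing Table 7.** The printed limits are one-sided 95% Clopper-Pearson upper limits, U(x, n) = Beta⁻¹(0.95; x + 1, n − x), with n = 120 and x = 120 times the printed rounded proportion.

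| Printed proportion | Computed limit | Table 7 limit | Limit minus proportion | Table 7 half-width |
|---|---|---|---|---|
| 0 | 0.02466 | 0.02466 | 0.02466 | 0.02466 |
| 0.0083 | 0.03887 | 0.03887 | 0.03057 | 0.03057 |
| 0.0167 | 0.05158 | 0.05158 | 0.03488 | 0.03488 |

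With whole-number counts, the limits for 1/120 and 2/120 are 3.89% and 5.15%. The comparisons below use whole counts on this scale.

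**Effect of early withdrawal.** Take 60 subjects (120 eyes) exposed to a lens, k of them withdrawn early with m affected eyes in total, and L events at week 2.

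- 2-week-visit reading of the plan: L / (120 − 2k)
- Any finding through week 2: (L + m) / 120

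| k | Affected eyes m | L | 2-week reading (upper limit) | Any finding through week 2 (upper limit) |
|---|---|---|---|---|
| 0 | 0 | 0 | 0/120 = 0% (2.47%) | 0/120 = 0% (2.47%) |
| 1 | 1 | 0 | 0/118 = 0% (2.51%) | 1/120 = 0.83% (3.89%) |
| 1 | 2 | 0 | 0/118 = 0% (2.51%) | 2/120 = 1.67% (5.15%) |
| 2 | 2 | 0 | 0/116 = 0% (2.55%) | 2/120 = 1.67% (5.15%) |
| 2 | 4 | 0 | 0/116 = 0% (2.55%) | 4/120 = 3.33% (7.47%) |
| 1 | 1 | 1 | 1/118 = 0.85% (3.96%) | 2/120 = 1.67% (5.15%) |

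**Direction.** With one affected eye per withdrawn subject (m = k), the 2-week figure is lower when L/(120 − 2k) < (L + k)/120. This simplifies to L + k < 60 and holds for any rare event. With both eyes affected (m = 2k), the condition is L + 2k < 120.

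**Replacement.** Sections 4.3 and 8.2 allow a discontinued subject to be replaced. With k = 1 and one replacement, the 2-week reading gives 0/120 (limit 2.47%), the same as a study with no event. Counting early findings gives 1/122 = 0.82% (limit 3.83%) for one eye, or 2/122 = 1.64% (limit 5.07%) for both.

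These limits treat eyes as independent, as Table 7 does. They show the size of the shift on the plan's own scale and are not offered as preferred intervals.

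**The case against.** **The endpoint might be cumulative.** An incidence after about two weeks can be read as cumulative through week 2. Section 14.5 names no visit, and 14.1 also says that all available data from scheduled visits will be used, which would include the 1-week visit. The text is therefore not beyond dispute. But However in 2.2 sets the endpoint apart from the other visits, the tables are split by event, and no rule carries a 1-week finding forward. Even on the cumulative reading, 14.1 still excludes unscheduled findings. If cumulative incidence is meant, the plan only needs to say so.

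**The Safety population might protect the estimate.** It decides which subjects are eligible for the analysis. It does not supply a 2-week observation for a withdrawn eye.

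**Early events are visible elsewhere.** This stands. They appear in the 1-week, unscheduled or final evaluation tables and in the adverse event listing, and missing counts are shown. A careful reader of a study this small could recover them. None of this changes the primary percentage.

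**A fixed-time percentage is a legitimate choice.** It is, but here the event itself prevents the fixed-time observation, so the percentage describes only the eyes still under observation.

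Two stronger readings are tempting and should not be drawn. A reader might infer that every Grade 3+ finding at an unscheduled visit forces withdrawal. It does not: step U.6 has no such rule, the Section 13.1 entry covers corneal findings only, 8.2 applies when the event requires stopping lens wear, and 13.3 leaves continuation to the investigator's judgment. A reader might also infer from Section 14.2 that the primary analysis is restricted to completers. That section sets a planning target; the analysis population is the Safety population in 14.5.

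**Conclusion.** The point holds as a conditional bias with a known direction. For the 1-week visit the route is firm under the 2-week-visit reading of 2.2: discontinuation is mandatory, and the available-data denominator with no imputation removes both eyes and the event. For unscheduled visits, exclusion from the primary analysis is stated outright, while loss of the 2-week examination depends on whether the subject is withdrawn.

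One subject with an early finding is enough to turn a true 0.83% or 1.67% into 0% and to lower the upper limit from 3.89% or 5.15% to 2.51%, about the full span of Table 7. These sizes assume 60 exposed subjects, no week-2 events and the stated number of early cases. The number that will occur is unknown; with none, the reported figure is correct. It would be wrong to conclude that the reported percentage will be biased, only that the rules allow it and give no protection. No formal decision turns on the figure, but it is the study's headline safety estimate, so the counting rule should be settled before database lock and unmasking.

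**What to change.** 1. In the synopsis endpoint, Section 2.2 and Section 14.5, define the primary percentage as eyes with any lens-related Grade 3+ finding from dispensing through the 2-week visit of that wear period. Count the 1-week visit, early-exit examinations, and unscheduled visits where a slit-lamp examination was done. All three places must change together; editing 14.5 alone would contradict 2.2.
2. Use as denominator the Safety-population eyes dispensed that lens with at least one post-dispensing slit-lamp examination in that wear period, so that unexamined eyes are not counted as event-free.
3. In Section 14.1, exempt this endpoint from the exclusion of unscheduled visits.
4. As supporting results by lens, report the 2-week-visit-only percentage and the number of eyes without a 2-week examination, with reasons.

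**Cost.** Wording in four places and a few supporting table rows. No new examinations are needed: slit lamp is already scheduled at every visit and at early exit unless just performed (step F.3), and step F.1 records the reason for discontinuation. The sample size is unchanged.

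**Downsides.** Some analysed eyes will have less than two weeks of exposure. Unscheduled slit-lamp data exist only where the examination was performed; step U.6 applies only if applicable, and resupply-only visits record dispensing alone. The stated incidence may be slightly less favourable. Reporting the 2-week-only figure alongside makes the difference visible.
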